**Date: 28/01/2018**

# **Acute Effects of Propylene Glycol/Glycerol Intake on Cardiorespiratory Blood Parameters**

## **Introduction**

The electronic cigarette is a device generating an aerosol from the "heating" of a liquid (e-liquid), which is inhaled (vaping). Propylene glycol (PG) and glycerol (GLY) are the two components for the vaporization of flavors and eventually nicotine . Its use is booming, in a context where the acute effects of inhalation of propylene glycol and glycerol, major components of e-liquid, are poorly known at the respiratory, metabolic and hemodynamic levels.

We emit the hypothesis that GLY and PG which have the same physicochemical properties, are deposited in the pulmonary alveoli and could alter lung gas exchange . Considering the hydrophilic properties of PG/GLY and their small sizes, we believe that there may be a passage of the GLY and the PG from the bronchial mucosa to the blood circulation . Once in the circulation, the PG/GLY are metabolized. GLY notably enters into pathways leading to formation of glucose and glycogen. It may also enter in the lipogenesis pathway . PG is metabolized by the liver to lactic and pyruvic acid .

We will test the following hypothesis: after inhalation of pure PG/GLY mix (50:50), arterial oxygen partial pressure decreases due to the deep-lung deposition of PG/GLY, which alter lung gas exchanges. We will also test the transcutaneous oxygen tension with the aim to highlight tissue hypoxia after acute nicotine free vaping. We will also assess the presence of metabolic disorders after inhalation of PG/GLY, by measuring the changes in pH, lactate, blood glucose, 2,3-bisphosphoglycerate and anion gap.

## **Material and Method:**

This is a randomized controlled trial, single blinded, at Saint-Pierre hospital (Université Libre de Bruxelles). Thirty patients will be prospectively recruited. The patient will be current tobacco smokers between 35 to 80 years old, who will undergo an elective coronarography. At the end of the coronarography procedure, if no significant incident has occurred, the arterial catheter will be left in place, and the patient will be taken to an adjacent room to the catheterization room for the study. The patient will be randomly assigned to the vaping group (inhalation of a liquid composed of 50% PG and 50% GLY (pharmaceutical grade), without flavors or nicotine) or placebo group (vaping with device turn off). In the vaping group, the patient will vape 1 gram of PG/GLY liquid, while in the placebo group, the participant will mimic vaping (15 puffs) (We initially intended to perform 35 puffs for the placebo vaping group but before initiating the study we decided to match the number of puff performed in the active group and in the placebo group).

The following interventions will be carried out:

- Arterial blood gas test, according to the following chronology: 1 before the start of the vaping, 2 after (at 5 and 20 minutes post-vaping). The samples will be taken thanks to the radial arterial catheter in a pre-heparinized syringe. The volume of the sample will be of 1 cc. The sample will

then be analyzed by an automaton (ABL90 FLEX - Radiometer). The parameters studied will be: arterial partial pressure in oxygen and carbon dioxide, pH, glucose and lactate. The other parameters calculated by the automaton will be: bicarbonate, ions and hemoglobin in its various forms (oxyhemoglobin, deoxyhemoglobin, carboxyhemoglobin and methemoglobin).

- Arterial blood sampling: according to the following chronology: 1 samples before the vaping and 2 after (at 20 minutes post-vaping). Arterial sampling will be realized thanks to the radial arterial catheter on an EDTA and SST tube, at the same time as the arterial blood gas. Four ml will be taken for each sample. At the end of the experimental session, the samples will be centrifuged at 3500g for 10 minutes, then they will be immediately aliquoted. The aliquots will be immediately stored in a refrigerator at -80 ° C for storage for future measurement of the 2,3-bisphosphoglycerate, CC16, SP-D and metabolomics analysis.
- Cardiac monitoring (IntelliVue MP40 - Philips), will consist of heart rate measurement as well as continuous electrocardiogram. The monitoring will be started before the first blood sample and before vaping to allow baseline measurements. It will be removed 20 minutes after vaping.
- Pulse oximeter (IntelliVue MP40 - Philips) will be used to measure the peripheral oxygen saturation. The pulse oximeter will be started before the first blood sample, before vaping. It will be removed at 20 minutes after vaping.
- The blood pressure will be assessed with an automatic sphygmomanometer (IntelliVue MP40 - Philips). The pressure will be assessed 3 times at 2-minute intervals, before vaping to allow baseline measurements. It will be measured again 3 times at 2 minutes intervals after vaping, as recommended by guidelines.
- A PeriFlux system 5000 (Perimed®, Järfälla, Sweden) will be used to explore the transcutaneous oxygen and carbon dioxide tensions by means of a PF 5040 unit and a dual transcutaneous O2 and CO2 tensions E5280 electrode. The micro-vascular perfusion in skin will also be assessed by a PF 5010 LDPM unit which measures the microvascular flow by means of a Laser Doppler. The device will be started before the first blood sample, at the same time as the pulse oximeter, and be removed 20 minutes after vaping.

The following outcomes will be studied:

- Arterial Gas partial pressure and saturation of oxyhemoglobin (PO)
- Anion gap, lactate, glycemia, pH, to complete the study of the saturation curve of the oxyhemoglobin (SO)
- Arterial 2,3-bisphosphoglycerate (SO)
- Arterial metabolomics analysis
- Blood Club cell 16 protein and Surfactant protein-D
- Skin microcirculatory blood flow study

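### No common smoke-, nicotine- and vape-free interval precedes the baseline sample and no time of last use is recorded, which risks added drift, chance imbalance and, in patients who also vape, a weakened effect

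*Combined protocol and SAP*

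**What the plan says.** Eligibility is a single sentence under Material and Method: "The patient will be current tobacco smokers between 35 to 80 years old", with the further requirement of an elective coronary angiography. The section gives no abstinence interval, no rule on e-cigarette use, and no instruction to ask when the patient last smoked or vaped.

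The session starts after catheterisation: "At the end of the coronarography procedure, if no significant incident has occurred, the arterial catheter will be left in place". One blood gas is taken before vaping and two after it, at 5 and 20 minutes. On allocation the text says "The patient will be randomly assigned to the vaping group", and the comparator inhales from a device that is switched off. Thirty patients are planned.

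The Introduction frames the question as the acute effect of the pure PG/GLY mix and adds: "We will also test the transcutaneous oxygen tension with the aim to highlight tissue hypoxia after acute nicotine free vaping". In the outcomes list, oxyhemoglobin saturation shares the primary line with the arterial gas pressures. Carboxyhemoglobin is among the hemoglobin fractions the analyser returns with each gas, but it is given no role in entry or analysis. The Statistical plan contains a sample-size statement based on the change in arterial oxygen pressure, with no analysis model and no covariates.

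**The concern.** The question is about an acute exposure, so the baseline should be clear of that exposure, or at least equally clear in every patient. As written, a patient who smoked shortly before admission and one who abstained overnight are both eligible. So is a smoker who also vapes and did so that morning. Nothing in the record would tell them apart, except that carboxyhemoglobin gives a partial view of recent smoking.

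Two mechanisms should be kept apart.

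- **Tobacco.** Wearing-off nicotine and carbon monoxide can move saturation, transcutaneous oxygen, skin flow, heart rate and blood pressure during the session by amounts that differ between patients. This is mainly noise.
- **Prior vaping.** The Introduction's own hypothesis is that PG/GLY deposits in the alveoli, passes into blood and is metabolised. If so, the single pre-vaping gas, lactate, glucose and metabolomics sample of a patient who recently vaped may already carry part of the effect under test. The measured change would then be too small, and randomisation does not restore what is lost.

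Neither can be repaired after the data are collected if time of last use was never asked.

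**Working it through.** **Inputs from the Statistical plan.** Difference in change 14 mmHg, SD 13 mmHg, two-sided alpha 0.05, power 80%, 14 per group. From Material and Method: 30 patients, so 15 per arm if allocation is equal.

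**Step 1: reproduce the stated size.** Normal approximation:

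n per group = 2 × (1.960 + 0.842)² × (13/14)² = 13.5, rounded up to 14.

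The plan's figure reproduces, with power 81.3% at 14. A two-sample t-test needs 14.56, hence 15 per group; its power is 78.3% at 14 and 81.2% at 15. The planned 30 patients therefore just meet the target, with almost no slack.

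This takes 13 mmHg as the SD of the change, although the plan describes it as the spread at baseline. With equal spread before and after, SD of change = 13 × √(2(1 − r)), which is 13 only if the before–after correlation r is 0.5.

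**Step 2: possible loss of effect from prior vaping.** The documents give no share of patients who also vape, no timing of last use and no size of carry-over, so every fraction here is an assumption. Write the average loss in the active arm as

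f = (share who also vape) × (share of those with recent use) × (share of the effect lost in them).

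For example, 0.20 × 0.5 × 0.5 = 0.05. A loss of 0.20 would need, say, one active patient in five to have vaped recently and to show no further fall at all. The remaining effect is 14 × (1 − f). t-test power with SD 13:

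| f (assumed) | Effect, mmHg | Power, 15 per arm | Power, 14 per arm | n per arm for 80% |
|---|---|---|---|---|
| 0 | 14.0 | 81.2% | 78.3% | 15 |
| 0.05 | 13.3 | 77.2% | 74.1% | 17 |
| 0.10 | 12.6 | 72.7% | 69.5% | 18 |
| 0.20 | 11.2 | 62.5% | 59.3% | 23 |

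The loss is treated as a shift in the mean only. A mixture of patients with and without a further fall would also widen the spread in the active arm, so power would be somewhat lower.

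**Step 3: chance imbalance.** Let each patient independently have recent exposure with probability p (assumed), 15 per arm. The probability that the arms differ by at least 4 patients (4/15 = 27 percentage points) is 0.03 for p = 0.10, 0.11 for p = 0.20, 0.16 for p = 0.30 and 0.20 for p = 0.50.

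**Step 4: tobacco drift.** The documents give no SD or target difference for saturation, transcutaneous oxygen, skin flow or the haemodynamic measures, so no power loss can be calculated for these.

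**The case against.** A reader might infer that the missing washout confounds the trial. The documents do not support that. Recent smoking or vaping happens before random assignment, the control is a "placebo group (vaping with device turn off"), and the powered comparison is the difference between groups in change. Prior exposure and any drift common to both arms are therefore balanced in expectation. This part of the objection stands in full.

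Nor is a diluted effect established. It requires a patient who also vapes, who did so close enough to the post-procedure baseline, who still carries an effect on oxygen pressure, and who then responds less to the study exposure. The documents quantify none of these steps, so the power losses are illustrations.

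Three further points stand. The tobacco mechanism bears on saturation, skin and haemodynamic measures more than on the powered oxygen pressure, and heart rate and blood pressure are measured but do not appear in the outcomes list. Carbon monoxide drift may also be small: assuming 5% carboxyhemoglobin at baseline, a half-life of 2 to 6 hours and a 30-minute session, the fall is 5 × (1 − 2^(−0.5/6)) = 0.3 to 5 × (1 − 2^(−0.5/2)) = 0.8 percentage points, in both arms. And it would be wrong to call an imbalance in recent smoking undetectable, because carboxyhemoglobin is read in every gas.

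The objection does not remove the gap itself. Time in the catheterisation room gives some smoke-free interval, but its length is unstated and not the same for all. Carboxyhemoglobin has no assigned use and would not reveal recent vaping.

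**Conclusion.** The point holds as a design gap, not as a source of systematic bias between the arms. A plan followed to the letter can take its only baseline sample after recent exposure to PG/GLY, nicotine or carbon monoxide, with no record of when. The consequences are patient-specific drift in saturation, skin and haemodynamic measures, a moderate risk of chance imbalance with about 15 per arm, and possible attenuation confined to patients who also vape.

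On the powered endpoint, the size depends wholly on assumed fractions. An average loss of 5% costs about 4 percentage points of power (81.2% to 77.2% at 15 per arm), and a loss of 20% costs about 19 (to 62.5%). These figures rest on a t-test, equal allocation and an SD of change of 13 mmHg. Because the design has almost no spare power and the remedy is cheap, the change is worth making.

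**What to change.** 1. In Material and Method, add one condition that applies to every patient: no smoking, nicotine product or e-cigarette use for a fixed interval before the pre-vaping sample. The investigators should choose and justify its length.
2. Before assignment, record the time of the last cigarette, the time of the last e-cigarette use, and whether the patient uses e-cigarettes regularly.
3. In the Statistical plan, prespecify adjustment for the baseline value of each outcome. Add baseline carboxyhemoglobin as a covariate for the saturation, skin and haemodynamic measures.
4. Prespecify a sensitivity analysis that excludes regular e-cigarette users.

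A carboxyhemoglobin cut-off for entry is not recommended. The documents support no particular value, and it would exclude patients after catheterisation, when the arterial line has already been left in for the study.

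**Cost.** One criterion, a few questions and a few lines of analysis plan; no new test, since carboxyhemoglobin is already measured. The downside is that smokers who do not comply must be replaced, and the results will describe smokers after a short abstinence. If the stated inputs hold, the planned 30 patients need not change on this account.

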#### Statistical plan

The objective of this study is to determine whether e-cigarette vaping decreases oxygen arterial blood concentration. Based on our previous researches, we assume that baseline mean arterial oxygen partial pressure will be 100 mm Hg with a standard deviation of 13 mmHg. To demonstrate that e-cigarette vaping significantly decreases arterial oxygen partial pressure, we assume a reduction in arterial oxygen partial pressure of more than 14 mm Hg. We will need 14 patients in each group, with

80% power to detect a group difference of 14 mm Hg in the change of arterial oxygen partial pressure at a two-sided alpha-level of 0.05.

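### Does setting the active arm by mass (1 gram) and the sham arm by count (15 puffs) undermine the puff-matched comparison?

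*Combined protocol and SAP*

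**What the plan says.** The exposure rules stand in one sentence of the Material and Method section: "the patient will vape 1 gram of PG/GLY liquid, while in the placebo group, the participant will mimic vaping (15 puffs", the latter with the device switched off. The same section explains that a larger sham count of 35 was dropped: "before initiating the study we decided to match the number of puff performed in the active group and in the placebo group". It gives no mass per puff, puff length, puff interval or session length, and does not say where 15 comes from.

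Arterial blood gases are taken as follows: "1 before the start of the vaping, 2 after (at 5 and 20 minutes post-vaping". The Statistical plan powers the study for "a group difference of 14 mm Hg in the change of arterial oxygen partial pressure".

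The measurements listed are blood gases, stored blood, ECG and heart rate, pulse oximetry, blood pressure, transcutaneous gas tensions and laser Doppler flow. Puff count and the start and stop times of vaping are not on the list. The documents do not say that they will go unrecorded; they are silent.

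**The concern.** The sham is there to separate the effect of inhaled propylene glycol and glycerol from the effect of puffing itself. For that, the two arms should go through much the same breathing manoeuvre for much the same time. The sponsor took this seriously enough to revise the sham count before starting.

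A rule in grams leaves the number of puffs free in the active arm. If active participants needed clearly more or fewer than 15 puffs, the arms would differ in breathing manoeuvre. They would also differ in time since baseline, because the baseline sample precedes vaping and the later samples are timed from its end. Such a difference arises after randomization, so randomization does not balance it. With no planned record of puffs or time, a reader of the results might be unable to see it. At stake would be a part of the oxygen difference that is due to the procedure and not to the aerosol.

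**Working it through.** **1. The plan's own figure.** Inputs from the Statistical plan: difference 14 mm Hg, SD 13 mm Hg (given for baseline, used here for the change), two-sided alpha 0.05, power 80%.

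n per group = 2(1.960 + 0.842)² × 13² / 14² = 13.5, rounded up to 14.

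This reproduces the stated 14 per group. No term depends on puff count, so the concern does not touch the sample size.

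**2. When the two rules agree.** 1000 mg / 15 puffs = 66.7 mg per puff. The rules do not contradict each other. The sham consumes no liquid, so only a count (or a time) can define it, and different units are unavoidable.

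**3. If 15 is the count expected for 1 gram.** Let mass per puff vary between participants as a log-normal with mean 66.7 mg and coefficient of variation c. The 10% and 20% values are assumptions; the documents give none. Then mean puffs = 15(1 + c²) and SD = c × 15(1 + c²).

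| c | Mean puffs | SD | 95% of participants | Mean minus 15 |
|---|---|---|---|---|
| 10% | 15.15 | 1.5 | 12.4 to 18.3 | 0.15 |
| 20% | 15.60 | 3.1 | 10.4 to 22.6 | 0.60 |

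Individuals differ, but the arm means nearly coincide: 0.15/15 = 1% and 0.60/15 = 4%. At an assumed 20 to 60 seconds per puff, the mean difference in elapsed time runs from 0.15 × 20 = 3 seconds to 0.60 × 60 = 36 seconds.

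**4. If the mean mass per puff is itself wrong.** At 10% off, 1000/60.0 = 16.7 puffs or 1000/73.3 = 13.6. At 20% off, 1000/53.3 = 18.75 (+3.75) or 1000/80.0 = 12.5 (-2.5). At the same 20 to 60 seconds per puff, the 20% case moves the samples 1.25 to 3.75 minutes later or 0.83 to 2.5 minutes earlier. This takes two stacked assumptions, and the first supposes that the sponsor's matching decision failed. Nothing in the documents points to that.

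**5. What it could do to the comparison.** The powered contrast is between group means. Variation between participants around nearly equal means adds spread; a systematic bias needs a difference in means. If the effect of puffing were proportional to the number of puffs (an assumption), the error carried into the contrast would be the mismatch divided by 15, times the change seen in the sham arm. That is 1% to 4% of the sham change in step 3, and 3.75/15 = 25% in the worst case of step 4. For 4% to equal the 14 mm Hg target, the sham alone would have to move arterial oxygen pressure by 14/0.04 = 350 mm Hg, against an assumed baseline of 100 mm Hg.

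**6. What the planned data already show.** The sham arm's change from baseline is measured, so the size of the puffing effect will be visible. Arterial carbon dioxide pressure is measured in both arms, and the skin electrode "will be used to explore the transcutaneous oxygen and carbon dioxide tensions by means of a PF 5040 unit" from before the first sample until 20 minutes after vaping. These give indirect information on ventilation, though not on puff count or duration.

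**The case for a change.** The strongest case for a change is that matching is the sponsor's own standard, and the plan gives no means of showing that it was met. A tally and a stopwatch cost almost nothing, and session times not noted on the day may not be recoverable. The indirect carbon dioxide measurements are no substitute, and no analysis of them for this purpose is planned.

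Part of this stands. The basis for 15 is not stated, and no record of puffs or vaping time is listed. Both would be useful detail.

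Two parts do not stand. First, silence in a protocol of a few pages is not evidence that nothing is recorded. Samples at fixed times after vaping, and monitors removed 20 minutes after it, oblige staff to know when each session ended; counting 15 sham puffs obliges them to count. Second, the harm is not shown. The documents give neither direction nor size for any effect of a few puffs or minutes on arterial oxygen pressure, and a sizeable mean mismatch has to be assumed.

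A stronger remedy, letting the sham count follow the accumulating active-arm counts, would make the control condition drift during enrolment and would still match only the average. That is a debatable trade-off about the exposure regimen, which is the sponsor's decision.

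**Conclusion.** No change to the plan is needed. Followed as written, it gives a sham whose puff count was set in advance to match the active arm, and a sound comparison of groups. What is missing is explanatory and operational detail that staff and analysts can sensibly supply: where 15 comes from, and the puffs and times noted at each session.

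The expected mismatch is 0.15 to 0.6 puffs in 15, provided that 15 is the count expected for 1 gram and that mass per puff varies by 10% to 20% between participants. The first condition is the natural reading of the text but is not stated outright; the second is an assumption. If the mean mass per puff were 20% off, the mismatch would be -2.5 or +3.75 puffs, but the documents do not support that premise. In neither case can an effect in mm Hg be derived, and the 14 per group is unaffected.

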#### Statistical plan

The objective of this study is to determine whether e-cigarette vaping decreases oxygen arterial blood concentration. Based on our previous researches, we assume that baseline mean arterial oxygen partial pressure will be 100 mm Hg with a standard deviation of 13 mmHg. To demonstrate that e-cigarette vaping significantly decreases arterial oxygen partial pressure, we assume a reduction in arterial oxygen partial pressure of more than 14 mm Hg. We will need 14 patients in each group, with

80% power to detect a group difference of 14 mm Hg in the change of arterial oxygen partial pressure at a two-sided alpha-level of 0.05.

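### The 80% power is claimed for the change in PaO2, but the only SD given is labelled baseline, and no SD of the change, correlation, analysis or post-vaping time is stated

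*Combined protocol and SAP*

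**What the plan says.** The Statistical plan of the combined protocol and SAP draws its inputs from the sponsor's own earlier research, without details: "we assume that baseline mean arterial oxygen partial pressure will be 100 mm Hg with a standard deviation of 13 mmHg". From these it derives 14 patients per group for "80% power to detect a group difference of 14 mm Hg in the change of arterial oxygen partial pressure", "at a two-sided alpha-level of 0.05". The section is one short paragraph; it names no test or model.

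Under Material and Method, recruitment is stated as "Thirty patients will be prospectively recruited". Arterial gases are timed as "1 before the start of the vaping, 2 after (at 5 and 20 minutes post-vaping" minutes' sampling, with the bracket closing there. The outcome list marks arterial gas partial pressure and oxyhaemoglobin saturation as primary and attaches no time to them. Neither that line nor the power statement says which post-vaping sample enters the change.

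**The concern.** The SD of a change is not the SD at baseline. It depends on the baseline SD, the post-vaping SD and the correlation between the two measurements, and the plan gives only the first. It may be well above or well below 13 mmHg, and power moves with it.

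Without the linking assumption, a reader cannot check whether 30 patients give the power claimed for the stated comparison, and a null PaO2 result would be hard to interpret. The open choice between the two post-vaping samples adds to this: the SD and the correlation may differ between 5 and 20 minutes, and so may the effect.

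**Working it through.** **Inputs from the documents.** Difference 14 mmHg in the change, SD 13 mmHg (labelled baseline), two-sided alpha 0.05, power 80%, 14 per group (all Statistical plan); 30 patients, one baseline and two post-vaping gases (Material and Method).

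**Assumptions, not in the documents.** All values of r; the post-vaping SD s (11, 13 or 15 mmHg); an equal split of the 30 patients, 15 per group. r = 0 is an extreme, since the samples share patient, catheter and analyser.

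**1. The plan's own figure.** Normal approximation with 13 as the SD of the quantity compared:

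n per group = 2 × (1.96 + 0.8416)² × (13/14)² = 13.54, rounded up to 14.

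The arithmetic is sound. By noncentral t with the same SD, power is 78.3% at 14 per group and 81.2% at 15. That 13 stood in for the SD of the change is inferred from this match; the plan does not say so.

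**2. What an unadjusted change score needs.** By noncentral t, 80% power for 14 mmHg requires an SD of the change of at most 12.73 mmHg (14 per group) or 13.21 mmHg (15 per group). With one post-vaping time and SD 13 before and after, SD of change = 13 × √(2(1 − r)), so the threshold is r = 1 − SD²/(2 × 169):

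- 14 per group: 1 − 12.73²/338 = 0.52
- 15 per group: 1 − 13.21²/338 = 0.48

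**3. Power at 15 per group, SD 13 at both times.** The baseline-adjusted analysis (ANCOVA) uses residual SD 13 × √(1 − r²) and 2n − 3 = 27 degrees of freedom, with the noncentral t averaged over chance baseline imbalance.

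| r | SD of change | Change score | Residual SD | Baseline-adjusted |
|---|---|---|---|---|
| 0 | 18.4 | 52% | 13.0 | 79.7% |
| 0.3 | 15.4 | 67% | 12.4 | 83% |
| 0.5 | 13.0 | 81% | 11.3 | 90% |
| 0.7 | 10.1 | 96% | 9.3 | 97% |

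With adjustment, the r needed for 80% falls to about 0.09 at 15 per group and 0.29 at 14.

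**4. Dependence on the post-vaping SD.** Here SD of change = √(13² + s² − 2r × 13s) and residual SD = s√(1 − r²). At 15 per group and r = 0, 0.3, 0.5, 0.7:

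- s = 15: change score 46/60/75/92%; adjusted 68/72/79.8/92%
- s = 11: change score 59/74/86/97%; adjusted 91/93/97/>99%

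Adjustment greatly reduces the dependence on r but not the dependence on s.

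**5. Limits of the comparison.** On this grid (s of 11, 13 or 15, r up to 0.7) adjustment is at least as powerful as the change score. Outside it, the change score can be slightly ahead: at s = 18.13 and r = 0.7, 81.5% against 80.0%.

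**The case against.** The best defence is that 13 mmHg may in fact be the SD of the change. The inputs come from the sponsor's earlier research, which a reader of the plan cannot see, and the sample size reproduces exactly on that footing. The samples are taken within one session from one catheter on one analyser, so r may well exceed 0.5. Thirty patients are planned against 28 required, and if the SD of the change is 13, 15 per group gives 81% even by noncentral t. On this view the matter is a reporting gap.

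Much of that stands. It is why a reader who infers from the 52% or 67% that the trial is underpowered, or that it needs more patients, goes further than the documents allow: they give no r and no post-vaping SD, so those percentages only show what the claim depends on. It would also be wrong to infer that the sample size was miscalculated.

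What does not stand is that the gap is closed. The text attaches 13 to baseline; if it is the SD of the change, the plan should say so. The two extra patients move the threshold r only from 0.52 to 0.48. And earlier research does not settle which post-vaping sample this trial will use.

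It can also be said that ANCOVA is a preference. It is not the only valid analysis, and it is not uniformly more powerful. It is recommended because it makes the result much less sensitive to the unstated r at almost no cost.

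**Conclusion.** The point holds in a limited form and should be fixed. The 80% claim is unsupported as written, because an SD labelled baseline is applied to a change without the assumption that links them, and neither the analysis nor the post-vaping time is named. It is not shown to be too low: true power may be above or below 80%.

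For an unadjusted change at one time with equal SDs, the claim rests on r of about 0.5 or more. A reader might take that as the condition for the trial as a whole; it is not, because the plan names no analysis and with baseline adjustment the threshold is about 0.09 at 15 per group (0.29 at 14) if the post-vaping SD is 13. These figures rest on the assumed r, the assumed post-vaping SDs and equal allocation.

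**What to change.** In the Statistical plan, name one post-vaping time (5 or 20 minutes) for the primary comparison, and analyse PaO2 at that time by ANCOVA on group with baseline PaO2 as covariate. Restate the power of the 30 patients on that basis, showing the assumed post-vaping SD and r.

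If the unadjusted change is kept, name the time, replace the baseline SD with the SD of the change (or r) from the sponsor's previous research, and restate the power. If neither figure is available, give power as a range over r.

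The cost is about two sentences and, for ANCOVA, one degree of freedom (27 instead of 28 at 15 per group). The stated power may become less favourable. No extra patients or samples are needed, and enrolment does not change.

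### No primary analysis model is named, and the only comparison described (change in PaO2) is usually less precise than one adjusted for the baseline PaO2 already being measured

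*Combined protocol and SAP*

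**What the plan says.** The Statistical plan consists of an objective and a sample-size calculation. The calculation assumes that "baseline mean arterial oxygen partial pressure will be 100 mm Hg with a standard deviation of 13 mmHg", and concludes: "We will need 14 patients in each group", for 80% power to detect a "group difference of 14 mm Hg in the change of arterial oxygen partial pressure" "at a two-sided alpha-level of 0.05". That sentence is the only description of the between-group comparison. It names no test, model or covariate, and it does not say which post-vaping sample defines the change.

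Material and Method schedules arterial blood gases once before vaping and at 5 and 20 minutes after it, so a baseline PaO2 is planned for everyone. The primary outcome line in the same section lists arterial gas partial pressure together with oxyhaemoglobin saturation and attaches no method of analysis. On numbers, it states: "Thirty patients will be prospectively recruited".

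**The concern.** Subtracting baseline is one way to use it, and it is the best way only if the true slope of post-vaping on baseline PaO2 is 1. If the slope is lower, which is the usual situation when baseline and follow-up SDs are similar, the change score carries extra noise that a covariate would remove. The trial is small and sits close to its 80% power target, so lost precision matters.

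The second issue is pre-specification. With no model and no time point named, there are at least four defensible primary PaO2 results: adjusted or unadjusted, each at 5 or 20 minutes. One of them could be chosen after the data are seen. The plan does not rule out adjustment; it leaves the choice open.

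**Working it through.** **Inputs from the Statistical plan:** two-sided alpha 0.05, power 80%, difference in change 14 mmHg, SD 13 mmHg (stated for baseline PaO2), 14 per group. **From Material and Method:** 30 patients, taken here as 15 per group. **Not in the documents:** the SD of change, the post-vaping SD and r. I assume 1:1 allocation and, unless stated otherwise, equal SDs before and after.

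**1. The plan's own figure.** n = 2(1.960 + 0.842)² × 13² / 14² = 13.54, so 14 per group. It reproduces if 13 is used as the SD of the change. By noncentral t, power is 78.3% at 14 per group and 81.2% at 15.

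**2. Implied correlation.** With SD s at each time, Var(change) = 2s²(1 − r). Setting both s and the SD of change to 13 gives 13² = 2 × 13² × (1 − r), so r = 0.5.

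**3. Relative precision.** The residual variance after adjustment is s²(1 − r²). Divided by 2s²(1 − r), this is (1 + r)/2. Estimating the slope multiplies the variance by 1 + 1/(2n − 4), which is 1.042 at n = 14 and 1.038 at n = 15. At r = 0.5 the ratio is 0.75 × 1.042 = 0.781 at n = 14 and 0.75 × 1.038 = 0.779 at n = 15, a 22% reduction. The ratio reaches 1 at r = 2/1.042 − 1 = 0.92 (n = 14) or 2/1.038 − 1 = 0.93 (n = 15).

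**4. Power for 14 mmHg with the SD of change held at 13.** Noncentral t, 2n − 2 df for change and 2n − 3 df for the adjusted model, the latter averaged over chance baseline imbalance. Change-score power is 78.3% at 14 per group and 81.2% at 15 throughout.

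| r | implied SD at each time | adjusted, 14 per group | adjusted, 15 per group |
|---|---|---|---|
| 0.3 | 11.0 | 91.4% | 93.3% |
| 0.5 | 13.0 | 87.2% | 89.6% |
| 0.7 | 16.8 | 82.9% | 85.7% |
| 0.9 | 29.1 | 78.6% | 81.7% |

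As r approaches 1, adjusted power at 14 per group falls to 76.6%. At r = 0.5, 80% power needs 12 per group with adjustment (80.9%) against 15 without (81.2%).

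**5. The same comparison with the SD at each time held at 13, 15 per group.** The SD of change is 13√(2(1 − r)) and the adjusted residual SD is 13√(1 − r²). The 95% CI half-width is 2.048 × SD × √(2/15) for change and 2.052 × SD × √(2/15 × 1.038) for adjusted.

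| r | SD, change / adjusted | power, change / adjusted | half-width (mmHg), change / adjusted |
|---|---|---|---|
| 0.3 | 15.38 / 12.40 | 67% / 83% | 11.5 / 9.5 |
| 0.5 | 13.00 / 11.26 | 81% / 90% | 9.7 / 8.6 |
| 0.7 | 10.07 / 9.28 | 96% / 97% | 7.5 / 7.1 |
| 0.9 | 5.81 / 5.67 | about 100% / about 100% | 4.3 / 4.3 |

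**6. Simulation check** (100,000 trials, 15 per group, r = 0.5): power 81.3% for change and 89.6% adjusted, variance ratio 0.776, and a mean estimate of −13.99 for both. Neither analysis is biased.

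**The case against.** The strongest reply is that nothing in the plan is wrong on efficiency grounds. A two-sided comparison of change is coherent and unbiased, its sample size reproduces, and baseline already enters through the subtraction. All of that is true, so this point is an improvement and not the correction of an error.

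The size of the gain is also uncertain. The value r = 0.5 is back-solved. The plan may simply have put the baseline SD into a two-sample formula, which says nothing about r. Samples taken minutes apart through one catheter could well be highly correlated. With the stated SD of 13 at each time and r of 0.7 or more, the power gain is only a point or two. The same reading cuts the other way at r = 0.3, where the change score falls to 67% power at 15 per group and adjustment restores it to 83%.

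The break-even near 0.92 depends on equal SDs. If the post-vaping SD were 1.2 times baseline (an assumption), the change score would be slightly more precise for r from about 0.68 to 0.92 at 14 per group. The loss is bounded, however. A fitted slope cannot leave more true residual variance than a slope fixed at 1, so the cost is at most the slope-estimation factor, about 4% of variance, plus one degree of freedom.

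Finally, powering on change does signal an intended comparison, and the two sampling times and the paired primary outcome are larger sources of open choice than the covariate. That is fair, and it is why the fix must name the time point as well. A sample-size sentence still does not specify an analysis.

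**Conclusion.** The point holds. No primary model, covariate or time point is specified, and the comparison that is described is usually less precise than one adjusted for baseline PaO2. At r = 0.5 with equal SDs, the gain is 22% of variance, about 8 to 9 points of power, and a 95% CI half-width of 8.6 instead of 9.7 mmHg at 15 per group. The gain is larger at lower r, fades to nothing near r = 0.9, and becomes a loss of under 2 points of power at worst. Because the documents do not give r or the post-vaping SD, the exact gain is unknown. The imbalance between a possible material gain and a very small loss does not depend on knowing it, and neither does the pre-specification gap. The change should be made, but the trial as planned is not invalid without it.

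**What to change.** Add two sentences to the Statistical plan before any outcome data are examined:

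- **Model.** The primary analysis is a linear model of post-vaping PaO2 on randomised group with baseline PaO2 as covariate, reporting the adjusted group difference with its 95% CI. Using the change as the response gives the same treatment coefficient once baseline is in the model.
- **Time point.** State which of the 5- and 20-minute samples is primary. If both are wanted, specify a repeated-measures model and the contrast to be tested.

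The unadjusted difference in change can be kept as a sensitivity analysis. The change needs no new samples and no more patients. It costs one degree of freedom and, in the least favourable case, under 2 points of power.
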